## **Scientific Background:**

Stroke is the most common neurological disorder in the U.S. (Roger, et al., 2012). 15-30% of stroke survivors are permanently disabled and 20% require institutional care (Mackay & Mensah, 2004). Upper extremity hemiparesis is one of the most common consequences of stroke and a major cause of disability and decreased quality of life in stroke survivors (Roger, et al., 2012). Existing rehabilitation techniques are frequently ineffective in restoring a sufficient amount of hand function in the affected limb to enable independent completion of daily tasks. Robotic therapies have been developed as an exercise tool for stroke survivors to utilize as an adjunct to conventional therapy. Therapeutic robots have the potential to deliver high-intensity task specific training, that may make them beneficial for stroke survivors with upper extremity hemiparesis (Chang and Kim, 2013). There are a variety of robotic devices that have been developed for upper limb rehabilitation after stroke, ranging from large workstations to lightweight wearable devices with a variety of control strategies. Most of these devices have focused on the shoulder, elbow or wrist, with relatively few focused on hand rehabilitation. MyHand is a unique device prototype that was developed in a collaborative project between faculty in the Columbia University Departments of Mechanical Engineering and Rehabilitation and Regenerative Medicine. MyHand is a noninvasive device that is worn on the forearm and hand. It contains motors and “exotendons” that physically assist with finger movements. The device can be controlled by surface EMG signals from the ipsilateral forearm or by a contralateral shoulder harness.

## **Study Objectives:**

Primary Research Question: Is the MyHand prototype effective at assisting stroke survivors to complete functional tasks with their upper extremity following a training period of 4 weeks?

Hypothesis 1: (Primary) We anticipate that there will be an improvement in functional use of the impaired upper extremity after training with MyHand.

Hypothesis 2 (Secondary): We anticipate that training with MyHand will improve strength and/or coordination in the impaired upper extremity as demonstrated by improvements in impairment based outcome measures.

## **Study Design and Methods:**

This is designed as a non-randomized interventional study of the effects of a 4-week training protocol with the MyHand device on functional and impairment based measures of upper extremity performance in stroke survivors with hemiparesis. Up to 24 community-dwelling chronic stroke survivors will be

recruited to participate in this study. Participants will complete the informed written consent process followed by screening procedures according to the following criteria.

Inclusion Criteria:

- Stroke diagnosis at least 6 months prior to start of study
- Passive range of motion: Wrist to neutral, Digits within normal limits
- Moderate muscle tone, i.e., Modified Ashworth Scale (MAS)  $\leq 2$  in digits, wrist, and elbow
- Active Range of Motion: At least 30 degrees shoulder flexion, 20 degrees shoulder abduction, 20 degrees elbow flexion, finger flexion within functional limits
- Strength: At least trace palpable finger extension
- Able to successfully flex the fingers to form a grasp
- Unable to extend the fingers fully without assistance
- Intact cognition to provide informed written consent

Exclusion criteria were:

- Concurrent participation in another study
- Comorbid orthopedic condition/pain limiting functional use of the impaired upper extremity
- History or neurological disorder other than stroke
- Excessive spasticity (Greater than 2 on the MAS)
- Recent Botox injection to the affected limb (< 13 weeks)

Participants will be assessed at baseline and after completing the 4-week training protocol with the following outcome measures: Fugl-Meyer Upper Extremity Scale (UEFM), the Action Research Arm Test (ARAT), the Box and Blocks Test (BBT), the Modified Ashworth Scale (MAS). For baseline measurements, all outcome measures will be performed without the assistance of the device. To evaluate rehabilitative and assistive effects of the training protocol, participants will complete post-testing assessments under two conditions over the course of two sessions to avoid fatigue. One session of post-testing will involve administration of the UEFM, ARAT, and BBT without robotic-assistance (unassisted condition), while the other session will involve administration of the ARAT and BBT with robotic assistance (assisted condition). The UEFM will only be performed at post-testing in the unassisted condition because the UEFM assesses capacity of the arm primarily through gross motor tasks, and comparatively few grasping and pinching tasks. We thus presume that robotic assistance will have minimal influence on FM scores. All outcome measures will be administered by an occupational therapist who is not involved in the training program.

Next, participants will be fitted with the MyHand device and screened with the EMG classifier to determine if they will use the EMG or shoulder harness control method. During the control screening, a classifier algorithm will be trained with the subject's EMG signals from the involved forearm. A participant will be assigned to the EMG control if they pass the classifier or the shoulder harness if they fail. Each participant will be trained to use their assigned control method.

The training protocol involves 12 sessions (3 sessions per week for 4 weeks). Each session will involve 30 minutes of active training time in which participants will practice a variety of grasp and release tasks with everyday objects to simulate Activities of Daily Living according to a standardized protocol. Participants who require additional upper extremity support to aid use of the device may be fitted with the commercially-available Saebo Mobile Arm Support to unweight the arm during training. Each training session will be supervised by a trained occupational or physical therapist. At the completion of

the training protocol, participants' upper extremity function will be reassessed with the outcome measures to evaluate if the MyHand device may have utility as rehabilitative and/or assistive device.

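### ARAT and BBT are never given with the device before training, so the assistive result belongs to the device in trained users and cannot be credited to the 4-week training protocol

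*Combined protocol and SAP*

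**What the plan says.** Under Study Design and Methods, every baseline test is unassisted: "For baseline measurements, all outcome measures will be performed without the assistance of the device". The next sentence gives the purpose of post-testing: "To evaluate rehabilitative and assistive effects of the training protocol, participants will complete post-testing assessments under two conditions". In the first condition, "One session of post-testing will involve administration of the UEFM, ARAT, and BBT without robotic-assistance (unassisted condition"); in the second, "the other session will involve administration of the ARAT and BBT with robotic assistance (assisted condition"). Which session comes first is not stated.

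Before the 12 training sessions the device is used only for set-up: "participants will be fitted with the MyHand device and screened with the EMG classifier to determine if they will use the EMG or shoulder harness". After that, "Each participant will be trained to use their assigned control method". No ARAT or BBT with the device is described at that point.

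The primary research question under Study Objectives is "Is the MyHand prototype effective at assisting stroke survivors to complete functional tasks with their upper extremity following a training period of 4 weeks". The primary hypothesis is "We anticipate that there will be an improvement in functional use of the impaired upper extremity after training with MyHand", without saying whether the test is assisted or unassisted. The last sentence of Study Design and Methods gives the purpose of reassessment as judging whether the device is useful for rehabilitation, for assistance, or for both.

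The Statistical Analysis Plan gives paired t-tests for UEFM and ARAT and a paired Wilcoxon test for BBT, at p < 0.05. It does not say which measurements form the pairs.

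**The concern.** An assistive effect of a training protocol is a change, brought about by training, in what people can do while wearing the device. Measuring that change requires a with-device score before and after training, and the plan collects only the second.

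Two quite different situations therefore give the same data. In one, the device gives its full help before the 12 sessions begin and the sessions add nothing to it. In the other, the help exists only because of the sessions. The sentence on post-testing attributes the assistive effect to training, which the data cannot support.

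There is also a reporting risk. Because the SAP leaves the pairs open, the assisted post-test could be paired with the unassisted baseline and the difference presented as a gain from training, although part or all of it may come from wearing the device during the test.

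**Working it through.** The plan states no figure to reproduce: the sample size (up to 24) comes without an effect size, SD or power. The check is whether each effect can be identified from the cells collected.

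**Cells for ARAT and BBT** (from Study Design and Methods)

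| | Without device | With device |
|---|---|---|
| Before training | B | A0, not collected |
| After training | U | A |

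UEFM has only B and U, so the point does not touch it.

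**Model for the cell means.** Let m be the unassisted baseline mean, r the unassisted change over training, d the device effect before training, and s the amount by which the device effect changes over training.

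- B = m
- U = m + r
- A0 = m + d
- A = m + r + d + s

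**What the collected cells give**

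- U - B = r
- A - U = d + s
- A - B = r + d + s, the sum of the two lines above

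Three cell means for four parameters give a design of rank 3. The change in assisted performance is A - A0 = r + s. It cannot be written as a combination of B, U and A, and neither can d or s alone.

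**Illustration with assumed scores** (not from the documents): B = 20, U = 22, A = 28. Then r = 22 - 20 = 2, d + s = 28 - 22 = 6, and A - B = 28 - 20 = 8. Each row below reproduces these three means exactly.

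| d | s | A0 = 20 + d | Change in assisted score, 28 - A0 |
|---|---|---|---|
| 6 | 0 | 26 | +2 |
| 0 | 6 | 20 | +8 |
| 8 | -2 | 28 | 0 |
| 9 | -3 | 29 | -1 |

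More participants would estimate 20, 22 and 28 more precisely but would not separate the rows. If A - B = 8 were reported as the training effect, only the 2 points of U - B would be a change measured without the device. The other 6 could be entirely device effect already present before training.

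**With the fourth cell.** A0 - B = d, A - A0 = r + s, and (A - U) - (A0 - B) = (d + s) - d = s. The design has rank 4 and all four parameters are identified.

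**The case against.** The strongest reply is that the attribution to training rests on one phrase. The primary question asks whether the device helps people after a training period, and the closing sentence of the methods asks whether the device is useful. Neither hypothesis poses a change in assisted performance. A - U and U - B are both collected and serve those aims. This stands. A reader might infer that the trial cannot answer its primary question, but the documents do not support that: A - U addresses it as worded. The remaining caution is session order. If all participants take the two post-tests in the same order, practice or fatigue between sessions is mixed into A - U.

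A second reply is that the intervention may be read as device plus training, so that A - B is simply the before-after change of the package. That is legitimate if it is labelled so. It does not justify calling the difference an effect of training.

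A third reply concerns an assisted baseline. The protocol splits post-testing over two sessions to avoid fatigue, so such a test would probably need its own visit. Taken after control-method training, it would already include that learning and would not show the effect at first fitting. With no control group, A - A0 would remain a before-after change. All of this stands, and it makes rewording the main remedy.

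A reader might also infer that the trial would lead to an unneeded 4-week course being recommended. No section makes or proposes such a recommendation.

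**Conclusion.** The point holds in a limited form. From the data the plan collects, the change in device-assisted ARAT and BBT over the 4 weeks cannot be estimated, whatever the sample size. Describing the assistive effect as one of the training protocol is therefore wrong as written. The device's effect in trained users can be estimated, so the primary question and the device-utility aim survive, subject to session order.

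The size of the error cannot be given in points, because the documents contain no scores; the scores in the illustration are assumed. The conclusion itself needs no numerical assumption. It rests on reading the protocol as giving no ARAT or BBT with the device before training, which the baseline sentence states directly. Classifier screening and control-method training involve the device, but they are not described as outcome tests.

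**What to change.** 1. In Study Design and Methods, restate the purpose of post-testing as *the rehabilitative effect of the training protocol and the assistive effect of the device in trained users*.
2. In the Statistical Analysis Plan, name the pairs for ARAT and BBT: post-unassisted versus baseline for the rehabilitative effect, and post-assisted versus post-unassisted for the assistive effect. State the order in which the two post-test sessions were given. If post-assisted versus baseline is shown at all, label it as the combined device-plus-training change.
3. Add a sentence saying that training's contribution to assisted performance cannot be estimated, because no assisted test was given before training.

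These are changes of wording only, and the cost is a less favourable claim. They are probably the feasible route, since the SAP is written in the past tense and reports normality results, which suggests that the data are already in.

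Only if enrolment is still open, an assisted BBT, with or without ARAT, could be added after control-method training and before session 1. The SAP would then add A - A0 and (A - U) - (A0 - B). This means at most 24 extra administrations of each test used, a probable extra session and one more test exposure per participant. It would measure the device effect after control training rather than at first fitting, and the change would still be an uncontrolled before-after comparison.

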#### **IRB-Approved Protocol Amendments Since 11/14/18**

- **12/10/18 Modification:** Study personnel change due to staff turnover
- **9/19/19 Modification:** Study personnel change due to addition of new PhD-student

#### **Statistical Analysis Plan**

We tested all the clinical outcome data and gains for normal distribution based on the residuals of our dependent variables with Shapiro-Wilk and visually with Q-Q plots. We also tested the homogeneity of variance using the Levene test. UEFM and ARAT passed normality and homogeneity test, and thus we applied paired sample t-tests. BBT failed the normality test. Therefore, we applied a nonparametric paired sample Wilcoxon test. Statistical significance was determined at  $p < 0.05$ .
